
2) Protocol Title

Partnering with WIC to prevent excessive weight gain in pregnancy

3) Investigator

[name], MPH

4) Objectives

a. Primary specific aim: To determine whether the healthy lifestyle program lowers the prevalence of excessive gestational weight gain, compared to usual WIC care. Primary hypothesis: Participants randomized to the healthy lifestyle intervention arm will demonstrate significantly lower prevalence of excessive gestational weight gain, compared to those randomized to usual WIC care.

b. Additional aims:

- i. To compare trial arms with respect to changes in diet and physical activity, and rates of adverse pregnancy outcomes (including glucose intolerance, hypertension, and infant macrosomia).
- ii. To utilize the RE-AIM framework to evaluate the intervention's dissemination potential in WIC. We will assess: reach into the patient population; effectiveness on outcomes; organizational adoption; consistency of implementation; and maintenance of effects on 6- and 12-month maternal/child postpartum weights.
- iii. To quantify the intervention's cost-effectiveness.

5) Rationale and Significance

Nearly two-thirds of pregnant women exceed Institute of Medicine (IOM) weight gain guidelines.¹ Excessive gestational weight gain not only adversely affects the current pregnancy – by increasing risk of diabetes and hypertension, cesarean delivery, and infant macrosomia – but it also promotes new or persistent obesity in women and their children.^{2,3} Ethnic minority women are at particular risk of greater gains because they are more likely to enter pregnancy obese,⁴ reside in obesogenic environments,⁵ and adopt obesity promoting behaviors (e.g., high caloric intake, physical inactivity).⁶⁻⁸ However, these high risk women also suffer from a paucity of treatments. Without intervention, the implications are clear: most will exceed recommended gains in pregnancy and incur significant morbidity for themselves and their children.^{9,10}

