- i. **Questionnaires.** Participants will complete several questionnaires at each time point (by phone or in-person, depending on participant preference and/or Covid-19 restrictions on in-person visits): Core Screening/Enrollment (CS/EN), 36-38 weeks' gestation (end of pregnancy), 6 months postpartum, and 12 months postpartum. All questionnaires will be read out-loud by study staff to minimize literacy demands. These questionnaires will contain the following items (with data collected and stored in REDCap):
 1. **Psychosocial measures:** Using previously validated questionnaires (merged into a single screening and follow-up survey), participants will self-report: 1) food security via the 6-item USDA survey, 2) health literacy via the BRIEF: Health Literacy Screening Tool, 3) quality of life via the Short Form 12 or SF-12, and 4) questions about housing stability.
 2. **Economics:** A variety of variables related to health insurance, work productivity, income, and hospital and outpatient visits will be collected to assess the cost-effectiveness of the intervention.
 3. **Sociodemographics:** A variety of variables will be collected via self-report, including age, parity, marital status, smoking history, and education.
 4. **Concomitant medications and adverse events:** At all visits, medications added/adjusted and adverse events will be recorded.
 5. **Infant feeding:** Infant feeding behaviors and beliefs will be assessed from questions adapted from the Infant Feeding Style Questionnaire at 6 month and 12 month postpartum visits.
 6. **Executive functioning:** Participants' executive functioning will be assessed using the BRIEF-A (Behavior Rating Inventory of Executive Function) at CS/EN.
 7. **Patient-provider interactions:** This will be assessed at the 36-week (end of pregnancy) visit and the 6-month postpartum visit via the MOR: Mothers on Respect Index and the MADM Scale: Mothers Autonomy in Decision Making.
- ii. **Weight and height.** Maternal weight will be measured at each time point either in-person or using a BodyTrace scale that will be sent to the participant after completion of the combined CS/EN call or visit. Height will be measured in-person or self-reported during the combined CS/EN call or visit.
- iii. **Infant weight and length.** With the participant's optional consent, we will have them sign medical record release forms to get their infant's weight and length from their pediatrician. These will be used to

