Effectiveness will be assessed via our primary, secondary and patient-centered outcomes.

Adoption is a measure of potential intervention uptake by WIC. We will quantitatively assess number of provider referrals for study entry.

Implementation will be examined on both the participant level and the WIC provider level. At the participant level, we will measure intervention engagement via: 1) number of responses to self-monitoring text prompts, text response time, and the type/frequency of texted videos viewed; 2) type/frequency of FB or Instagram posts and/or likes; and 3) number/duration of WIC provider visits and calls completed. Relying on an approach by Olson and colleagues, we will examine the extent to which level of engagement is associated with gestational weight gain.⁸⁵ We will also evaluate the consistency of the intervention across different patient/provider subgroups. At the WIC provider level, we will examine process data stored in our web application and perform chart reviews to assess documentation of weight-related counseling to measure intervention delivery fidelity.

Maintenance of weight change will be assessed at 6- and 12-months postpartum. We will determine the proportion of women in each treatment group at (+/- 0.9kg) or below early pregnancy weight by 6 months and 12 months postpartum. While observational data repeatedly suggest that excessive gestational weight gain is the strongest predictor of postpartum adiposity,³ few studies have evaluated this relationship in the context of a clinical trial. With participant consent, we will additionally abstract their infant's weight and length from their pediatrician visits. These will be used to approximate measures at 6-months and 12-months of age and assess maintenance of intervention effects on infant weight/length.

iii. **Data analysis plan:**

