1. **Primary aim.** We will use Fisher's exact test (for raw intervention effects) as well as multivariable logistic regression (for adjusted intervention effects), testing the effect of treatment group on the odds of excessive gestational weight gain while simultaneously adjusting for covariates discovered to be unbalanced between the trial arms at baseline. We will consider interaction effects of treatment by relevant baseline predictors when needed, (e.g., age, parity, BMI, and gestational age at enrollment), to evaluate the assumption of equal intervention effects between the 2 arms with respect to these covariates. Data will be analyzed using an intention-to-treat (ITT) approach where subjects are analyzed according to their treatment assignment at randomization, regardless of level of engagement. Since an ITT analysis is planned, 2 methods are proposed for accounting for missing data. First, multiple imputation methods will be used to estimate weight at 36-38 weeks' gestation based on intermediate outcomes, mediating variables, and data collected on subjects with complete follow-up.^{87,88} A second approach will utilize model-based analyses with direct maximum likelihood methods.⁸⁹

Additionally, to take advantage of the longitudinal nature of this study, we will treat weight as a continuous measure, employing an advanced mixed-effects modeling approach to estimate individual and mean weight trajectories over time by treatment group. We will supplement weights collected by research staff with available electronic health record prenatal weight data abstracted from WIC and/or participants' obstetric records; we and others have found that the absolute agreement between research and prenatal clinic measured weights is extremely high, providing strong support for exchangeability.^{90,91} Benefits of this modeling approach include: 1) ability to accommodate all available measured prenatal weight data; 2) allowance for varying and/or unequally-spaced intervals between measurements; and 3) high variability in the number of longitudinal assessments expected across subjects. Longitudinal trajectories could be modeled using splines or kernel density.⁹² They will allow for an unbiased estimation of the overall intervention effect on gestational weight gain to better understand non-linear, dynamic changes in weight over time.

2. **Additional aims.** We will use parallel strategies to those described above for secondary and patient-centered outcomes.

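### The maternal maintenance outcome is defined only as a proportion; adding the difference in postpartum weight in kg is a nearly free gain in precision

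*Combined protocol and SAP*

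**What the plan says.** Section 4.b.ii lists, as the last RE-AIM component, "maintenance of effects on 6- and 12-month maternal/child postpartum weights". Section 9.d.ii.5 (RE-AIM outcomes, Maintenance) then says for mothers: "We will determine the proportion of women in each treatment group at (+/- 0.9kg) or below early pregnancy weight by 6 months and 12 months postpartum". For children, the same paragraph takes weight and length from pediatric visits to "assess maintenance of intervention effects on infant weight/length", with no cut-off.

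The data for a continuous maternal analysis exist. Section 9.b.ii states "Maternal weight will be measured at each time point", and Table 1 marks maternal weight at the baseline, 6-month and 12-month visits.

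A continuous weight model appears in 9.d.iii.1, under the primary aim: "we will treat weight as a continuous measure, employing an advanced mixed-effects modeling approach". Its first listed benefit is "ability to accommodate all available measured prenatal weight data", and its stated product is "unbiased estimation of the overall intervention effect on gestational weight gain". Postpartum weight is not mentioned there. Section 9.d.iii.2 applies parallel strategies to the secondary and patient-centered outcomes, the heading under which RE-AIM is listed, and then says that RE-AIM outcomes will be explored. The power calculation in 9.d.iii.4 concerns the primary outcome only.

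**The concern.** A yes/no count treats all women on the same side of the cut-off alike. A woman who retains 2 kg and one who retains 15 kg are the same failure. If the intervention lowers retained weight among women who stay above the cut-off, the proportion does not move.

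The plan already guards against this for its binary primary outcome, by adding a continuous weight analysis. It names no counterpart for maternal maintenance. If the proportion were all that was reported, the estimate of the postpartum effect would be less precise than the collected data allow. A kg analysis added later would also be open to the charge of having been chosen after the data were seen.

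**Working it through.** **1. The plan's own figure.** Section 9.d.iii.4 assumes 40% against 55%, two-sided alpha 0.05 and power 0.80. The two-proportion formula gives 173 per arm without and 186 with continuity correction, so the stated 186 reproduces. Exact Fisher power at 186 per arm is 0.811, and 0.969 for 40% against 60%, in line with the stated 0.8 and 0.96. Allowing for 15% loss, 186/0.85 = 218.8, hence 219 per arm. None of this refers to maintenance, for which the plan states no power.

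**2. Information kept by the cut-off.** Let p be the proportion meeting it and z_p the matching normal quantile. For a normal outcome with a location shift, the efficiency of the proportion relative to the mean difference is φ(z_p)² / [p(1 − p)].

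| p | φ(z_p)² / [p(1 − p)] | Efficiency | Loss | 186 per arm is worth |
|---|---|---|---|---|
| 50% | 0.1592 / 0.25 | 0.637 | 36.3% | 118 |
| 40% | 0.1493 / 0.24 | 0.622 | 37.8% | 116 |
| 30% | 0.1209 / 0.21 | 0.576 | 42.4% | 107 |
| 20% | 0.0784 / 0.16 | 0.490 | 51.0% | 91 |

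The loss is smallest at p = 50%, where it equals 1 − 2/π = 36.3%.

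The documents give neither p nor an SD, so p was also derived from assumed values as Φ((0.9 − mean)/SD). With mean retention 3 kg and SD 6 kg, p = Φ(−0.35) = 36.3% and the loss is 39.1%. Over means of 0 to 5 kg and SDs of 5 to 8 kg, the loss runs from 36% to 50%.

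**3. What this does to power.** Power serves here only as a yardstick of precision. Binary power is exact Fisher power, enumerated over both binomials. Continuous power is from the noncentral t. The intervention-arm proportion is Φ(z_p + d) for a shift of d SD. At p = 40% and d = 0.30 this is Φ(−0.253 + 0.30) = 51.9%.

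| Women per arm | d | p, usual care | Proportion | Mean difference |
|---|---|---|---|---|
| 186 | 0.30 | 40% | 0.61 | 0.82 |
| 164 (219 × 0.75, i.e. 25% lost) | 0.30 | 40% | 0.54 | 0.77 |
| 186 | 0.25 | 30–50% | 0.42–0.45 | 0.67 |
| 186 | 0.35 | 30–50% | 0.71–0.74 | 0.92 |

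**4. Sensitivity to the distribution.** Simulation used 20,000 trials, 186 per arm, a 0.30 SD shift and 40% meeting the cut-off under usual care. Power for the proportion against the mean difference was:
- right-skewed gamma(4): 0.68 against 0.82
- t with 10 df: 0.68 against 0.82
- t with 5 df: 0.79 against 0.83

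For a cut at the median of a t distribution, the efficiency is 4 f(0)² × variance, where f is the density. The loss is 31% with 20 df, 24% with 10 df, 12% with 6 df and 4% with 5 df. With 4 df the efficiency is 1.125, so the ordering reverses. The one-third figure is therefore a result of the normal model and not a property of this trial's data.

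**The case against.** The case for leaving the plan alone is substantial.

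- **The aim contradicts the outcome.** A reader might infer this, but section 4.b.ii names no unit, mean or estimand. The proportion of women back at early-pregnancy weight is a legitimate effect on postpartum weight, and it has the same form as the primary outcome. There is no contradiction.
- **The whole maintenance aim is dichotomised.** It is not. Infant weight and length carry no cut-off, so the point concerns mothers only.
- **A continuous analysis is ruled out.** It is not. Section 9.d.iii.2 could carry the mixed model over to postpartum weight. But that text governs how outcomes are analysed and does not add one. Applied to the outcome as defined, it leads most directly to Fisher's test and logistic regression. It gives permission, not a commitment.
- **The trial is underpowered for maintenance, or will wrongly declare that effects were not maintained.** The plan claims no power for this exploratory outcome and sets no significance rule for it. The power figures above measure relative precision and show no broken promise.
- **Over a third of the information is certain to be lost.** That needs near-normality and the proportion as the sole analysis. The documents establish neither.

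These objections remove the stronger readings. What remains is that the only maternal measure named is the less precise one under most plausible distributions, and that the better one needs no new data.

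**Conclusion.** The point holds in limited form. Maternal maintenance is defined only as a proportion, and no continuous analysis of postpartum maternal weight is committed to. If the proportion is the sole analysis and weight change is roughly normal, at least 36% of the information on the maternal comparison is lost, and more as p moves away from 50%. The loss is smaller with heavy tails and can vanish.

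The usual-care proportion, the shift and the distribution are all assumptions. The primary analysis, the sample size and the infant part of maintenance are unaffected. This is a worthwhile improvement to an exploratory outcome and not a defect that threatens the trial's conclusions.

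**What to change.** In 9.d.ii.5, add a second maternal measure: the between-arm difference in maternal weight (kg) at 6 months and at 12 months. Estimate it by a mixed model or ANCOVA that adjusts for baseline weight and the randomisation strata (weight status and ethnicity, section 8.c.vii), with a 95% CI at each visit. Report it alongside the existing proportion and state that both remain exploratory. It would help to say in 9.d.iii.2 that this analysis is the intended extension of the continuous weight model to the postpartum visits.

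The cost is a sentence or two and one extra model on weights already being collected. It needs no new measurement and no extra participants, and the proportion is still reported.

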 2. Pre-existing medical condition and/or medication that could influence weight (e.g., diabetes, HIV, thyroid disorder, bulimia, anorexia, gallbladder disease)
 3. Diagnosis contraindicating weight control (e.g., hyperemesis gravidarum)
 4. Shared phone
 5. Multiple pregnancy (e.g., twins)
 6. Current and/or previous participant of our Temple-led obesity treatment interventions in pregnancy or the postpartum period

7. Serious or unstable medical or psychological conditions that, in the opinion of the investigator, would compromise the subject's safety for successful participation in the study

e. Study Timelines

- i. The duration of a subject's participation in the study: Approximately 18 months. Participants will be followed for one year after delivery.
- ii. The duration anticipated to enroll all subjects: approximately 30 months.
- iii. The estimated date that the investigators will complete the study: December, 2023.

9) Study Procedures and Data Analysis

- a. Data collection: This section reviews the types of data that will be collected, stored, and analyzed to meet the scientific goals of the study. Trained research staff will collect assessments for participants in intervention and usual care arms at multiple time points (Table 1). Our evaluation protocol will be similar to the ones we have used successfully in prior trials. If transportation is an issue, we will conduct visits at participants' homes.
- b. We will additionally abstract data from participants' WIC records and obstetric charts, including 24-28 week oral glucose tolerance test (OGTT) results, prenatal weights, and infant birth weight at delivery. We have used this pragmatic approach to collect high-quality data from medical records in prior studies.^{19,28} A detailed study timetable and list of all procedures at each visit are shown below:

Table 1: Summary of types of data collected

Measure	WIC/Phone Screening	Time point			
		CORE Screening/ Enrollment (CS/EN)	36-weeks' Gestation	6-Mo Postpartum	12-Month Postpartum
		Baseline	Follow-up 1	Follow-up 2	Follow-up 3
Screening Eligibility Form	X				
Informed Consent		X			
Questionnaires		X	X	X	X
Maternal Weight	X	X		X	X
Maternal Height	X	X		X	X
Infant Weight				X	X
Infant Length				X	X
ASA-24: 24-Hour Recall of Food Intake		X	X		
Maternal Medical Record Review		X	X	X	X
WIC Medical Record Review		X	X	X	X

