approximate measures at 6-months and 12-months of age and assess maintenance of intervention effects on infant weight/length.

- iv. **24 Hour Dietary Recall (ASA-24).** Measures of dietary intake via electronic 24-hour recalls administered at combined CS/EN call or visit and at the end of pregnancy visit. More details are provided in the data analysis section below.
- v. **Medical record review.** With the participant's consent, we will extract information about her medical history to confirm eligibility, health problems and weight during pregnancy, delivery records, and postpartum records.

WIC record review. With the participant's consent, we will extract information about nutritional topics/issues discussed at WIC visits occurring during the study period. We will extract maternal and infant weight and height data collected at WIC visits during the study period. We will also extract any changes to participants' address(es) and phone number(s) collected at WIC.

- c. **Treatment:** This section reviews the two treatment arms in the study.
 - i. Eligible volunteers will be randomly assigned by Temple study staff, with use of a random-number generator in RedCap, to a treatment group consisting of either usual WIC care (SC) or an individual, healthy lifestyle intervention (AO) that consists of: 1) empirically supported behavior change goals; 2) self-monitoring of behavioral diet goals and weight gain via text messages with automated feedback; 3) tailored skills training materials; and 4) WIC nutritionist counseling.
 - ii. **Description of SC:** Participants assigned to the WIC usual care arm will receive usual care offered to pregnant women at WIC. Per WIC protocol, participants will be strongly encouraged to schedule routine prenatal care visits with their obstetricians, who will be informed of the patient's participation (but not randomization assignment) via letter (included in the original submission). We will ensure that WIC providers have access to self-help materials (e.g., brochures from the American College of Obstetricians and Gynecologists [ACOG]) and quarterly trainings on obesity treatment updates). Additionally, all participants randomized to SC will receive self-help materials compiled from American College of Obstetricians and Gynecologists [ACOG].

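### The exploratory 6- and 12-month weight-maintenance outcome takes no account of a new pregnancy, and no listed questionnaire item records one

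*Combined protocol and SAP*

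**What the plan says.** All references are to the combined protocol and SAP.

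- **Aim.** Section 4.b.ii includes among the additional aims an assessment of "maintenance of effects on 6- and 12-month maternal/child postpartum weights".
- **Definition.** Section 9.d.ii.5 (Maintenance) will report the "proportion of women in each treatment group at (+/- 0.9kg) or below early pregnancy weight by 6 months and 12 months postpartum". It gives no exclusion, censoring or sensitivity rule for a new pregnancy.
- **Duration.** Section 8.e: "Participants will be followed for one year after delivery".
- **Weighing.** Section 9.b.ii: "Maternal weight will be measured at each time point either in-person or using a BodyTrace scale". Pregnancy status is not a condition. Under section 6.b, assessments are by phone unless public health guidance and the participant allow an in-person visit.
- **Questionnaires.** Section 9.b.i lists psychosocial, economic, sociodemographic, medication and adverse-event, infant-feeding, executive-function and patient-provider items. The nearest to pregnancy status is parity, in a self-report list "including age, parity, marital status, smoking history, and education".
- **Other sources.** Table 1 schedules maternal medical record review and WIC record review at 6 and 12 months. Section 9.b.v says the medical review covers "health problems and weight during pregnancy, delivery records, and postpartum records". Section 9.b.i.4 adds: "At all visits, medications added/adjusted and adverse events will be recorded".
- **Status.** Section 9.d.iii.2 makes the RE-AIM analyses exploratory.

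**The concern.** The outcome is meant to measure whether a woman has lost the weight she gained in the study pregnancy. A woman well into another pregnancy at the 6- or 12-month weighing carries weight from that pregnancy, and the margin is only 0.9 kg. Read literally, the definition classifies her like anyone else, so the reported proportion mixes weight retention with repeat pregnancy.

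The practical problem is timing. With phone visits and a home scale, staff may not see that a woman is pregnant. If status is not asked when she is weighed, it may not be recoverable afterwards. At stake is the interpretation of the maintenance result: understated return to weight in both arms and a somewhat diluted difference.

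**Working it through.** **1. The plan's own figures.** No expected proportion, sample size or repeat-pregnancy rate is given for maintenance. The only sizing (section 9.d.iii.4) is for the primary outcome: 40% vs 55%, two-sided alpha 0.05, power 0.8.

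- Without continuity correction: n = [1.96 × √(2 × 0.475 × 0.525) + 0.8416 × √(0.40 × 0.60 + 0.55 × 0.45)]² / 0.15² = 173 per arm.
- With continuity correction: 186 per arm, as stated.
- After 15% loss: 186 / 0.85 = 218.8, so 219 per arm, as stated.

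These figures reproduce, and the present point does not touch them.

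**2. Effect on the maintenance proportions.** Let p be the true proportion returned to weight and q the share pregnant again at the visit. Assume q is equal in both arms, is unrelated to whether a woman would otherwise have returned to weight, and that every such woman is counted as not returned. Then:

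- observed proportion = p × (1 - q)
- observed difference = true difference × (1 - q)

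For an illustrative true 50% vs 40%:

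| q (assumed) | Higher arm | Lower arm | Difference (points) |
|---|---|---|---|
| 0% | 50.0% | 40.0% | 10.0 |
| 5% | 47.5% | 38.0% | 9.5 |
| 10% | 45.0% | 36.0% | 9.0 |
| 15% | 42.5% | 34.0% | 8.5 |

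These are upper bounds on the shrinkage at each q, because not every woman pregnant again will exceed the margin.

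**3. Effect on power.** This borrows 186 per arm and a 15-point difference (55% vs 40% returned to weight) from the primary sizing, for scale only. Power uses the normal approximation without continuity correction.

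| q (assumed) | Difference if all counted as not returned | Power | Power if those women are excluded (15 points kept) |
|---|---|---|---|
| 0% | 15.0 | 0.83 | 0.83 |
| 2% | 14.7 | 0.81 | 0.82 |
| 5% | 14.3 | 0.79 | 0.81 |
| 10% | 13.5 | 0.75 | 0.79 |
| 15% | 12.8 | 0.71 | 0.76 |

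If only half of those women are misclassified, the 15-point difference becomes 15 × (1 - q/2), which is 14.9 points at q = 2% and 13.9 at q = 15%.

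**4. If q differed by arm.** With 10% in the intervention arm and 5% in usual care: 0.55 × 0.90 - 0.40 × 0.95 = 11.5 points. Reversed: 0.55 × 0.95 - 0.40 × 0.90 = 16.3 points. Nothing in the documents suggests such a difference; this shows only that counts by arm are worth having.

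**The case against.** **Failure is not automatic.** A reader might infer that every woman pregnant again is scored as having failed. The plan contains no such rule. She misses the criterion only if she is more than 0.9 kg above early-pregnancy weight, and that comparator is itself a pregnancy weight: enrolment is at up to 16 weeks, and section 9.d.i places the baseline weight in the first or early second trimester. A woman early in a new pregnancy is compared with herself at a broadly similar stage. This stands, and confines the problem mainly to women further along.

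**Some pregnancies will come to light.** A reader might also infer that new pregnancies cannot be identified. That is too strong. Record reviews are scheduled at both postpartum visits, medication changes and adverse events are recorded at each, and healthcare use is surveyed. Later pregnancies, where weight matters most, are the likeliest to appear in records. The full questionnaires are not in the documents and the sociodemographic list is open-ended, so only the listed items can be judged. This stands in part. No section says a new pregnancy will be sought, dated against the weighing or used, and even a known one has no stated handling.

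**Bias between arms is speculative.** The documents do not support a link between the intervention and birth spacing. Goal rotation ends with the end-of-pregnancy visit (section 9.c.iii.1), and no active postpartum treatment is described.

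**The effect is small and the outcome exploratory.** At 186 per arm, the 95% half-width for 50% vs 40% is 1.96 × √[(0.25 + 0.24)/186], about 10 points, against an attenuation of at most 1.5. This stands and sets the severity.

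**The remedy has a statistical cost.** Setting aside weights from a new pregnancy conditions on a post-randomisation event, which sits uneasily with the intention-to-treat approach. This also stands, so the measured weights should be analysed as well.

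**Conclusion.** The concern holds in a limited form. The maintenance outcome ignores new pregnancy, no listed questionnaire item records it at 6 or 12 months, and other sources may reveal it but are not assigned that purpose. Following the plan therefore mixes repeat pregnancy into weight retention to an unknown but probably modest degree.

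The upper bound is the factor (1 - q): a 10-point difference reads as 9.5 to 8.5 points at q of 5% to 15%. This assumes equal q in both arms, independence from return to weight, and misclassification of every such woman. The range for q is an assumption.

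The documents do not support reading this as a fixed failure rule, an undetectable event, a demonstrated bias between arms or a threat to the trial's main conclusion. The outcome is exploratory, and the primary outcome and sample size are unaffected. It is a cheap improvement of low severity.

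**What to change.** 1. Add a current-pregnancy question to the 6- and 12-month surveys in both arms.
2. State in section 9.d.ii.5 that a weight taken during a new pregnancy is not assessable for maintenance, and handle it with the plan's missing-data methods. Section 9.d.iii.1 spells these out only for the 36-38 week weight, so say explicitly that they extend to the postpartum weights.
3. Report the number pregnant at each visit by arm.
4. Give a sensitivity analysis that keeps all weights as measured.

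Replacing the value with the last non-pregnant weight is not recommended as the main rule, because that weight could date from any time since delivery.

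**Cost.** One survey item and a few sentences. Some values become missing: at the assumed 5% to 15%, about 19 to 56 of 372 women (372 × 0.05 = 18.6; 372 × 0.15 = 55.8). The main maintenance analysis would also depend on a post-randomisation event, which is why items 3 and 4 belong with it.
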